Hypothesis: The feasibility of the incentives intervention will be evaluated based on several metrics including counseling call completion rates (≥ 3 completed), follow-up assessment completion rates ($\geq 75\%$), smoking cessation rates at the 12-week follow-up ($\geq 25\%$ biochemically-verified 7-day point prevalence abstinence), incentive costs, and positive perceptions of the intervention.

Aim 2. To evaluate the potential efficacy of OTH+I relative to OTH alone.

Hypothesis: Individuals randomly assigned to the OTH+I will complete more counseling calls and achieve higher rates of biochemically-verified abstinence at the 12-week follow-up than those assigned to OTH alone.

The current study will generate preliminary data for a full-scale research proposal to evaluate the impact of offering a financial incentives program for OTH callers with the goals of increasing smoking cessation treatment uptake and cessation rates in PPCs, and reducing tobacco-related cancer incidence and mortality.

Note, the original study protocol planned to gather biochemically-verified abstinence using carbon monoxide breath samples. Due to a technical difficulty, breath samples will not be gathered from participants and study staff will gather self-reported smoking status. Upon data analysis, the research team will take the above specified aims to evaluate the feasibility of and need of gathering biochemically-verified abstinence in such interventions.

B. Background and Significance

Smoking prevalence rates are disproportionately high among adults of low SES,⁴ and socioeconomic disadvantage is associated with a reduced likelihood of smoking cessation.⁵⁻¹⁰ The incidence of lung cancer, a disease primarily caused by smoking, is far greater among those with less education and those living in poverty relative to their higher socioeconomic status (SES) counterparts.^{11,12} Although individuals of lower SES are just as likely to initiate quit attempts, they are less likely to succeed.¹³ Likewise, smoking cessation interventions for low-SES adults have produced very low abstinence rates at follow-up.¹⁴⁻¹⁷ Treatment approaches are needed to target socioeconomically disadvantaged people specifically and to reduce barriers to smoking cessation.

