
Data collection will occur remotely via telephone, and web- and smartphone-based surveys from the OTH and the OUHSC.

M. Statistical Methods

In our previous research, smoking abstinence rates were 14% vs. 33% for SC (counseling + pharmacotherapy) and SC plus incentives, respectively, at the 12 week post-quit-date follow-up in safety net hospital patients,¹⁴ and preliminary findings are similar at 12 weeks post-quit-date (13% vs. 35%, N=235) in our ongoing randomized controlled trial (PI: [name]; R01CA197314). Assuming a two-sided alpha of 0.05, a sample of 250 participants (80 per group) will offer 80% power to detect an 18% difference in cessation rates between OTH and OTH+I at the 12-week follow-up if we assume abstinence rates of 12% vs. 30%. This sample size would also offer 80% power to detect a small effect size of intervention group (OTH vs. OTH+I) on the number of counseling calls completed (0-5 calls possible).

Feasibility (Aim 1). The feasibility of offering treatment-related incentives via the OTH will be evaluated based on several metrics including the total number of counseling calls completed (0-5 possible), with the goal of achieving an average ≥ 3 completed counseling calls, and a follow-up rate of $\geq 75\%$ based on follow-up rates in our previous³⁰ and ongoing trial (PI: [name]; R01CA197314). As in other CM studies,^{60,62,66,67,68} an intent-to-treat approach will be used in which participants who do not demonstrate biochemical verification of abstinence will be classified as smoking (i.e., *no need to account for loss to follow-up*). We will characterize intent-to-treat smoking cessation rates at the 12-week follow-up, with the goal of achieving $\geq 25\%$ biochemically-verified 7-day point prevalence abstinence in the incentives group. Participant perceptions of the intervention will be characterized, as well as the costs associated with counseling- and abstinence-contingent incentives.

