Potential Efficacy (Aim 2). Logistic regression analyses will be conducted to evaluate the influence of OTH vs. OTH+I on biochemically-confirmed 7-day point prevalence smoking abstinence (binary) at 12 weeks (primary outcome) post-enrollment which is 4 weeks after incentives have ended. Linear regression analyses will be conducted to evaluate the influence of treatment group on the number of counseling calls completed. However, if the number of counseling calls completed is not normally distributed, we will explore the use of other models such as Poisson, negative binomial, or zero-inflated models. Covariates in the analyses may include age, sex, race/ethnicity, nicotine dependence, insurance status, annual household income, and/or educational attainment.

Note, the original study protocol planned to gather biochemically-verified abstinence using carbon monoxide breath samples. Due to a technical difficulty, breath samples will not be gathered from participants and study staff will gather self-reported smoking status. Upon data analysis, the research team will take the above specified aims to evaluate the feasibility of and need of gathering biochemically-verified abstinence in such interventions.

N. Data and Safety Monitoring Plan

The Program Leaders ([name], [name]) will be responsible for all data monitoring and for compliance with all federal and OUHSC IRB policies and procedures for monitoring progress, safety, reporting of unanticipated problems or adverse events, and assuring actions resulting in suspension of the study are reported.

Because this proposal reflects a pilot/feasibility study, a formal Data Safety and Monitoring Board (DSMB) is not required. The program leaders will be responsible for monitoring rates of enrollment, risks of participation, protocol adherence by the research team, safety and confidentiality of data collection, data entry, and statistical issues. Relevant unanticipated problems, adverse events, or participant concerns will be reviewed by the program leaders. The OUHSC IRB will be informed of any findings. All modifications to the protocol will be submitted for IRB approval. Changes to or errors in the protocol will be promptly disseminated to study personnel via e-mail, and retraining procedures will be implemented as needed. Appropriate modifications will be made in consultation with the designated program person at the National Institutes of Health if necessary.

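### Breath samples were dropped in favor of self-report, but the Aims, intent-to-treat rule, 25% goal and primary outcome still require biochemical verification

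*Combined protocol and SAP*

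**What the plan says.** **Text that drops verification.** Identical notes after the Aims (Section A) and at the end of Section M say that "breath samples will not be gathered from participants and study staff will gather self-reported smoking status". The Abstract compares self-reported abstinence at 12 weeks. Section D, Measures, collects self-reported smoking status by web questionnaire at 4, 8 and 12 weeks. Section D, Measurement of Abstinence, removes the breath-sample payments.

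**Text that still requires it.** Five operative statements were left as they were:

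- Aim 1 criterion (Section A): at least 25% with "biochemically-verified 7-day point prevalence abstinence), incentive costs, and positive perceptions of the intervention".
- Aim 2 hypothesis (Section A): the incentives group will "complete more counseling calls and achieve higher rates of biochemically-verified abstinence at the 12-week follow-up than those assigned to OTH alone".
- Intent-to-treat rule (Section M, Feasibility): "participants who do not demonstrate biochemical verification of abstinence will be classified as smoking", from which the plan concludes "no need to account for loss to follow-up".
- Goal (Section M, Feasibility): at least 25% "biochemically-verified 7-day point prevalence abstinence in the incentives group".
- Primary outcome (Section M, Potential Efficacy): the "influence of OTH vs. OTH+I on biochemically-confirmed 7-day point prevalence smoking abstinence (binary) at 12 weeks (primary outcome) post-enrollment".

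The notes redefine none of these. They add only that the team will use the aims to "evaluate the feasibility of and need of gathering biochemically-verified abstinence in such interventions".

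**The concern.** The primary outcome is defined by a measurement that the same section says will not be made. This is current text, not a record of superseded wording: the protocol was approved on April 17, 2023, about 11 months after the May 19, 2022 enrollment date that Section D uses to separate the payment schedules.

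The intent-to-treat rule matters most. It did two jobs: it defined who counts as abstinent, and it disposed of missing data, because anyone lost to follow-up had no verification and so counted as smoking. Without verification, the stated reason for not accounting for loss to follow-up goes too, and nothing is written in its place for a participant with no 12-week self-report.

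The yardstick also moves. The Background states that the 13% vs. 35% precedent was biochemically verified. A 25% goal met on unconfirmed report is a more lenient test than one met on verified abstinence, and the plan does not say so.

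**Working it through.** **1. The plan's own figure.** Inputs from Section M: 12% vs. 30%, two-sided alpha 0.05, 80% power, 80 per group. With pooled variance under the null:

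n = [1.96 × √(2 × 0.21 × 0.79) + 0.8416 × √(0.12 × 0.88 + 0.30 × 0.70)]² / 0.18²
= [1.129 + 0.473]² / 0.0324 = 79.2, so 80 per group.

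Power at 80 per group is 80.4%. The figure reproduces, so this point is about the outcome definition and not about the power calculation. Printing 250 participants beside 80 per group is a separate matter.

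**2. The rule as written.** With no breath samples, nobody can demonstrate verification. Abstinent: 0 of n in each arm, 0% vs. 0%. The logistic regression has no events, no odds ratio can be estimated, and 0% is below 25% whatever participants report.

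**3. What the missing-status rule is worth for the 25% goal.** This compares missing counted as smoking with a responders-only denominator, at the plan's 75% follow-up target.

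| Incentives arm | Responders | Needed, missing = smoking | Needed, responders only | Counts where the choice decides |
|---|---|---|---|---|
| 80 (stated) | 0.75 × 80 = 60 | 0.25 × 80 = 20 | 0.25 × 60 = 15 | 15 to 19 |
| 125 (assumed equal split of 250) | 0.75 × 125 = 93.75, taken as 94 | 0.25 × 125 = 31.25, so 32 | 0.25 × 94 = 23.5, so 24 | 24 to 31 |

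For example, 15 abstainers are 15/80 = 18.75% or 15/60 = 25.0%, and 19 are 19/80 = 23.75% or 19/60 = 31.7%.

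**4. What it is worth for the group comparison.** Take 12% vs. 30% as the rates with missing counted as smoking, and assume 75% follow-up in both arms. Among responders the rates are 0.12/0.75 = 16% and 0.30/0.75 = 40%.

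- Odds ratio, missing = smoking: (0.30/0.70)/(0.12/0.88) = 3.14.
- Odds ratio, responders only: (0.40/0.60)/(0.16/0.84) = 3.50.
- Pooled z, 80 per arm: 0.18/√(2 × 0.21 × 0.79/80) = 2.80.
- Pooled z, 60 responders per arm: 0.24/√(2 × 0.28 × 0.72/60) = 2.93.

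The conclusion is the same either way. Unequal follow-up between arms could matter more, but the documents give no figures for it.

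**5. The other outcomes.** Call completion, follow-up and perceptions do not depend on verification. Cost does: Section M includes abstinence-contingent incentives in it, and Section D pays \$50 on self-reported abstinence at 8 weeks to those enrolled before May 19, 2022. The stated \$290 maximum is fully used by questionnaires (50 + 3 × 30 = 140) and calls (20 + 25 + 30 + 35 + 40 = 150), which leaves no abstinence payment for later enrollees.

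**The case against.** The best defense is that nobody would apply the text literally. The switch is disclosed twice, once directly below the primary analysis. The Abstract was updated and the questionnaires collect self-reported status. On this view the leftover wording is an incomplete edit in a pilot study, and a result with no events is a reading rather than a risk. Most of this stands: self-report is the evident intent, and the change is not concealed.

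Two further parts stand. The notes change only how abstinence is ascertained. Nothing withdraws the 7-day window or the 12-week time point, so a reader who infers that the window is now open goes further than the text allows. And the plan commits to intent-to-treat cessation rates, so counting missing as smoking is the natural carry-over. A responders-only analysis is proposed nowhere and would conflict with that commitment. The count ranges in the working therefore show what an explicit sentence is worth; they are not two readings of equal standing.

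The 25% goal is also one of several feasibility metrics, with no stated go/no-go rule attached.

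The defense does not supply the missing text. Evident intent is not a definition, the two endpoints remain side by side, and the only written rule for non-responders depends on a measurement that no longer exists.

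**Conclusion.** The point holds as an unreconciled definition. Five operative statements, including the primary outcome, require verification that the plan says will not be obtained. Followed exactly, they give 0% vs. 0%, no odds ratio and an unattainable goal. Under the evident intent the analysis can be done, and the remaining gap is the unwritten rule for participants with no 12-week self-report. That gap is worth 5 abstainers on the 25% goal in an arm of 80 (20 against 15), assuming 75% follow-up. It is worth little on the group comparison (odds ratio 3.14 or 3.50, assuming 75% follow-up in both arms).

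A reader might infer more, and the documents do not support it:

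- The outcome was not switched silently; the notes disclose it.
- No bias from misreporting can be sized, because the documents give no misreporting rate.
- Not all the supporting rates can be called verified. That is stated for 13% vs. 35%, but not for 14% vs. 33%, and the 12% vs. 30% planning rates are not labeled either way.

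The carbon monoxide wording left in Sections G, K, N and P is clerical.

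**What to change.** In the Aims and Section M:

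1. Define the primary outcome as self-reported 7-day point prevalence abstinence at 12 weeks post-enrollment, and use the same definition in the Aim 1 criterion and the Aim 2 hypothesis.
2. Replace the verification rule with: participants with no 12-week self-report of abstinence are classified as smoking.
3. Replace the statement about loss to follow-up with a commitment to report follow-up by arm.
4. Label the 25% goal as self-reported, and note that the 13% vs. 35% precedent was biochemically verified, so the goal now applies to a more lenient outcome.
5. State that abstinence payments within the cost outcome were made on self-report, to those enrolled before May 19, 2022.

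Separately, the sponsor should reconcile the Study Overview in Section D, which judges potential effectiveness by call completions, with the Abstract and Section M, which use abstinence. It names no primary outcome, so which is meant is for the sponsor to say.

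The cost is wording and one table. Follow-up completion at 12 weeks is already to be documented, and no new data are needed if the 12-week questionnaire already asks about the past 7 days, which the documents do not show. The changes are best made before outcome data are examined. The downside is that conclusions are limited to self-reported abstinence.

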[name], Ph.D. (Program Co-Leader) is an Assistant Professor in the OUHSC Department of Pediatrics and Director of the OTH. [name] is an affiliate of the HPRC, and he offices at the HPRC in order to facilitate communication and collaboration between the HPRC and the OTH. [name] oversees the state helpline contract with Optum, which is the OTH operator.

[name], MD (Co-investigator) is a Professor in the Department of Family and Preventive Medicine, and Associate Director of Community Outreach and Engagement at the NCI-Designated SCC. [name] is an affiliate of the TSET HPRC, and he offices at the HPRC to facilitate communication and collaboration. [name] research focuses on rural and tribal health, including tobacco use (e.g.,⁴⁶⁻⁵⁰). He will assist with rural and tribal outreach and recruitment efforts.

[name], Ph.D. (Co-Investigator) is an Assistant Professor in the OUHSC College of Public Health, within the Department of Biostatistics and Epidemiology and a member of the TSET HPRC. She has a history of tobacco-focused and other collaborations with [name] (Program Leader).^{43, 51-55} She will provide biostatistics support for the study.

D. Research Design and Methods (What, When, How, Where)

Study Overview. The proposed randomized controlled trial will enroll 250 adults who are seeking smoking cessation treatment through the OTH and who reside in any of the 16 PPCs in Oklahoma. Participants will be randomly assigned to OTH *or* OTH plus escalating incentives (OTH+I) for completing up to 5 counseling calls over 8 weeks. Feasibility outcomes for the incentives-based intervention will focus on counseling call completion, follow-up assessment completion, smoking cessation, incentive costs, and perceptions of the intervention. Potential effectiveness will be evaluated based on comparisons of counseling call completions at 12 weeks post-enrollment (4 weeks after incentives have ended) in OTH+I relative to OTH alone.

Randomization Plan. Randomization will be stratified by sex (male vs. female), race/ethnicity (White vs. non-White), and cigarettes smoked per day (≤ 10 vs. > 10).

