Interventions. Eligible OTH callers will be randomly assigned to one of two treatment groups: OTH or OTH+I. OTH care will include up to 5 counseling calls with a Tobacco Treatment Specialist and eight weeks of NRT. Note that an additional 6 weeks supply of NRT will be provided beyond the 2-week supply typically offered by the OTH to ensure that all participants receive adequate pharmacotherapy. OTH+I will include all components of OTH care plus escalating incentives for completing up to 5 counseling calls over 8 weeks (at least one week apart). Based on the incentive schedule used in our current (PI: [name], R01CA197314) and past research,^{29,30} incentives will start at \$20 for completing the first call, and will increase by \$5 for each consecutive call completed until the 5th call is completed (i.e., up to \$40 may be earned for completing the 5th call). The incentive will reset to \$20 if a call is missed (i.e., not completed within 2 weeks of the prior call). OTH treatment group participants may receive up to \$140 and OTH+I treatment group participants may receive up to \$290.

Contingency Management (CM). CM participants will receive counseling and nicotine replacement therapy (as described above). They will receive financial incentives for completing counseling calls.

Measurement of Abstinence.

Participants enrolled prior to May 19, 2022 who self-report smoking abstinence at 8 weeks post enrollment will receive the abstinence payment of \$50 as specified in the initial study application. Because breath samples will not be gathered as specified in the initial protocol, these participants may not receive the \$20 breath sample payments. Participants who are enrolled after May 19, 2022 will follow the payment schedule as outlined above in the protocol (payments for questionnaires, incentive group will also receive payments for counseling calls), and the payments for breath samples will be removed. In total, the standard care group will be eligible for up to \$140. In total, the standard care plus financial incentives group will be eligible for \$290.

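### The linear model for calls completed hangs on a normality condition that a 0-5 count cannot literally meet, and the count models then opened come with no rule for which result is reported

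*Combined protocol and SAP*

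**What the plan says.** Section M (Potential Efficacy, Aim 2) names the default: "Linear regression analyses will be conducted to evaluate the influence of treatment group on the number of counseling calls completed". It then qualifies it: "if the number of counseling calls completed is not normally distributed, we will explore the use of other models such as Poisson", with negative binomial and zero-inflated models also listed. Covariates are optional: "Covariates in the analyses may include age, sex, race/ethnicity, nicotine dependence, insurance status, annual household income, and/or educational attainment".

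The range of the outcome is fixed elsewhere. Section M gives 0 to 5 as the possible number of calls, and section D (Interventions) caps both groups, since "OTH care will include up to 5 counseling calls with a Tobacco Treatment Specialist" and the incentive arm adds payment for the same calls.

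The outcome matters to the trial. More calls under incentives is half of the Aim 2 hypothesis in section A. The Study Overview in section D bases potential effectiveness on call completions. Section M, however, attaches the primary label to 12-week abstinence.

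No section gives a normality test or cut-off, an order among the alternatives, a fit criterion, the type of standard error, or a rule for which estimate is reported.

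**The concern.** A condition that cannot literally be met is no condition. The analyst can set the named model aside in any dataset, and the choice among at least four models is made after the data are seen.

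The models named as replacements also carry a risk that the linear model does not. An ordinary Poisson model takes the variance to equal the mean. If the true variance is smaller, its standard errors are too large and power is lost. If the true variance is larger and this is ignored, they are too small and false positives rise. Negative binomial can repair only the second case, because it can only add variance.

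The pilot is meant to supply preliminary data for a full-scale proposal. A missed gain in calls, or a result that depends on the model picked, would carry into it.

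**Working it through.** **The plan's own figure.** Section M claims 80% power for a small effect on calls but gives no effect size, mean or SD. It cannot be reproduced and says nothing about the distribution. All shapes below are therefore assumptions.

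**Inputs from the documents.** Range 0-5; two-sided alpha 0.05; 80 per group as section M states, and 125 per group if 250 are split equally. Both sizes were run; that mismatch is a separate matter.

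**Step 1: is the condition ever met?** In simulated residuals for all ten shapes below at 80 per group, Shapiro-Wilk rejected in 100% of runs (300 per shape), including the symmetric binomial(5, 0.5). The plan names no test, so this only illustrates a strict check.

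**Step 2: type I error.** Let φ = variance/mean. The model-based Poisson standard error is too large by about 1/√φ, so its type I error is about 2[1 − Φ(1.96/√φ)]. For φ = 0.40: 1.96/0.632 = 3.10, giving 0.2%. For φ = 2.10: 1.96/1.449 = 1.35, giving 17.6%. Simulation (20,000 replicates per cell, 125 per group; linear is an unequal-variance comparison of means) agrees:

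| Assumed P(0)…P(5) | Mean | φ | Poisson, formula | Poisson, simulated | Linear, simulated |
|---|---|---|---|---|---|
| U: .28 .14 .08 .08 .12 .30 | 2.52 | 1.69 | 13.2% | 12.7% | 4.8% |
| Strong U: .38 .10 .04 .04 .06 .38 | 2.44 | 2.10 | 17.6% | 17.7% | 4.8% |
| Binomial(5, .5) | 2.50 | 0.50 | 0.6% | 0.6% | 5.3% |
| Low-skewed: .25 .30 .20 .12 .08 .05 | 1.63 | 1.26 | 8.1% | 8.1% | 5.1% |
| Stop after call 1: .05 .40 .20 .12 .08 .15 | 2.23 | 1.05 | 5.6% | 5.5% | 5.0% |
| Flat | 2.50 | 1.17 | 7.0% | 6.6% | 4.7% |
| Binomial(5, .6) | 3.00 | 0.40 | 0.2% | 0.2% | 5.0% |
| Ceiling: .03 .05 .07 .15 .25 .45 | 3.89 | 0.46 | 0.4% | 0.4% | 4.9% |
| U, higher mean: .20 .10 .08 .10 .12 .40 | 3.04 | 1.32 | 8.8% | 8.7% | 5.2% |
| Left-skewed: .08 .10 .14 .20 .24 .24 | 3.14 | 0.78 | 2.6% | 2.7% | 4.9% |

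Over both sample sizes linear stayed within 4.7-5.3%.

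**Step 3: power.** The only mean the plan states is the feasibility target, "with the goal of achieving an average ≥ 3 completed counseling calls", which belongs to the incentives intervention. So the incentives group is set at 3 and the control group below it. Take binomial counts, 80 per group, means 2.50 and 2.99.

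- Linear: variances 1.25 and 5 × 0.598 × 0.402 = 1.20; SE = √((1.25 + 1.20)/80) = 0.175; 0.49/0.175 = 2.80; power Φ(2.80 − 1.96) = 80%.
- Poisson, log scale: ln(2.99/2.50) = 0.179; model SE = √(1/(80 × 2.50) + 1/(80 × 2.99)) = 0.0958; z = 1.87. The true SE is √(1.25/(80 × 2.50²) + 1.20/(80 × 2.99²)) = 0.0647, which is 0.675 of the model SE. Power is Φ((1.87 − 1.96)/0.675), about 45%.

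Simulation with the incentives mean at 3.0 gives Poisson 43-45% for binomial shapes and 78-92% for the others, where linear has about 79%. The values well above 79% arise where Poisson is also too liberal under no effect, so they are not a gain. Poisson with robust standard errors keeps 78-80%.

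**Step 4: free choice among models.** A separate run took the smallest p-value from linear, Poisson, negative binomial and zero-inflated Poisson at 125 per group. Type I error was 12.2% for a U-shape, 6.7% for a right-skewed shape and about 6% for two others (600 runs, error about 1 point; many negative binomial and zero-inflated fits did not converge on underdispersed data).

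**The case against.** The best defense is that the text is flexible, not wrong. Linear regression stays the default, exploring other models does not oblige anyone to switch, and the open list excludes neither a bounded model nor robust errors. An analyst who read the condition as approximate normality could keep the linear model for near-symmetric counts, which is where Poisson loses most. All of that stands, and it limits the claim to what the wording permits. It does not supply a reporting rule.

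Three stronger readings are tempting, and the documents do not support them.

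- *A large general loss of power.* If a count model is picked by AIC and the control group already averages 3 or more calls, simulated power is 25-53% for the four shapes with mean of at least 3. But the plan states no AIC rule, and the target of 3 is for the incentives intervention, not a control mean. With the incentives mean at 3 instead, the same assumed rule gave about 44%, 62%, 43% and 66% for those shapes (80 per group, 200 replicates, error about 3.5 points).
- *The 5-call cap as the fault.* Count models do ignore the cap, but so does linear regression, and Poisson with robust errors performs well while still unbounded. The fault is the model-based standard error together with the choice made afterwards.
- *General inflation of type I error, or damage to the primary result.* Poisson is far too conservative for some shapes and too liberal for others, and section M gives the primary label to abstinence.

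**Conclusion.** The point holds in this form. The normality condition cannot literally be met, is not needed at these sample sizes, and opens an unruled choice among models, some of which can give wrong error bars. With model-based errors, Poisson type I error ranges from about 0.2% to 13-18% over the assumed shapes. With an incentives mean of 3, its power is about 44% against 80% for binomial counts, with little or no loss for low-skewed, stop-after-one-call, flat or left-skewed shapes.

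These sizes rest on assumed distributions; which one applies here, and so the direction of any error, is unknown. This is a pilot and calls is not the outcome labelled primary, so the change should be made but does not put the trial in question. Confidence is high on the missing rule, which can be read from the text, and medium on its consequence.

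**What to change.** Before calls are compared by group, delete the normality condition in section M and write, for example:

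*Calls completed (0-5) will be analyzed by linear regression on treatment group and the randomization strata (sex, White vs. non-White, cigarettes per day ≤10 vs. >10) with heteroscedasticity-robust standard errors, whatever the distribution. The result is the difference in mean calls with its 95% CI. Ordinal, binomial or count models are sensitivity analyses only; any Poisson model will use robust standard errors. The 0-5 distribution will be tabulated by group.*

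The strata are named because "Randomization will be stratified by sex (male vs. female), race/ethnicity (White vs. non-White), and cigarettes smoked per day", while the optional covariate list leaves cigarettes per day out. Simulated under assumed prognostic strata and blocks of 4, with HC3 errors, this model had type I error of 4.1-5.9% (average 4.9%; 2,500 replicates per cell) and power of 74-82% (600 per cell) where the target was about 80%. An ordinal or binomial model fixed in advance would also remove the later choice; linear is proposed because the plan names it first and its result is in calls.

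The cost is a wording change, since "All modifications to the protocol will be submitted for IRB approval", and the loss of freedom to choose the model after seeing the data. No new data or participants are needed. A mean difference does not show where in the 0-5 range the groups differ; the table covers that.

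### The Aim 2 models need not include the three randomization factors: sex and race/ethnicity are optional covariates, and the cigarettes-per-day factor is not listed

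*Combined protocol and SAP*

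**What the plan says.** Section D, Randomization Plan: "Randomization will be stratified by sex (male vs. female), race/ethnicity (White vs. non-White), and cigarettes smoked per day", the last split at 10 or fewer vs. more than 10. That is three binary factors, or eight cells. No block size, allocation method or allocation ratio is given.

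Section M, Potential Efficacy (Aim 2), names a logistic regression for 12-week abstinence, the primary outcome. For the second outcome, "Linear regression analyses will be conducted to evaluate the influence of treatment group on the number of counseling calls completed", with Poisson, negative binomial or zero-inflated models as fallbacks. The paragraph then states "Covariates in the analyses may include age, sex, race/ethnicity, nicotine dependence, insurance status, annual household income, and/or educational attainment".

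That sentence is all the document says about covariates. Nothing requires a stratification factor in either model, describes a stratified analysis, or gives a rule for choosing among the seven variables.

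**The concern.** Set side by side, the two sections do not match:

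| Randomization factor (section D) | Status in the Aim 2 models (section M) |
|---|---|
| Sex | Optional |
| White vs. non-White | Race/ethnicity is optional, coding not given |
| ≤10 vs. >10 cigarettes per day | Not listed |

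Nicotine dependence is listed, but it is optional, its measure is undefined, and it is not the cigarettes-per-day factor.

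Stratified allocation removes most of the chance imbalance on these factors. If they predict the outcome, a treatment-only model still counts their variation as noise. Its standard error is then somewhat too large for the design, its test falls below the nominal 5%, and it forgoes power. If the factors do not predict the outcome, little is lost.

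A lesser point is that seven optional covariates allow 2^7 = 128 models, and their conditional odds ratios will differ. The study is meant to supply preliminary data for a full-scale proposal, so one defined estimate is preferable.

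**Working it through.** **1. The plan's own figure.** Inputs from section M: two-sided alpha 0.05, power 80%, 12% vs. 30%. The pooled two-proportion formula uses p̄ = 0.21:

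n = [1.96·√(2·0.21·0.79) + 0.842·√(0.12·0.88 + 0.30·0.70)]² / 0.18² = (1.129 + 0.473)² / 0.0324 ≈ 79.2, so 80 per group.

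The stated 80 per group is reproduced (power 80.4%), with no strata in the calculation. At 125 per group (250 split equally) power is 94.2%. Both sizes are carried below because the text states both.

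**2. Abstinence model.** Logistic Wald test with 10,000 simulated trials per scenario, treatment only vs. treatment plus the three factors. The following are assumptions, because the documents do not give them:
- equal allocation in permuted blocks of 4 within the eight cells;
- 50% of each sex and 65% smoking more than 10 per day;
- 32% non-White, which is the section B figure for county residents, applied here to callers;
- the factor odds ratios in the table.

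| Assumed odds ratios (sex / race / cigarettes) | Power at 250, unadjusted | Power at 250, three factors |
|---|---|---|
| 1 / 1 / 1 | 94.6% | 94.7% |
| 0.8 / 0.7 / 0.5 | 94.8% | 95.1% |
| 0.6 / 0.5 / 0.33 | 95.4% | 96.1% |
| 0.5 / 0.4 / 0.25 | 95.2% | 96.3% |

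Each figure has a simulation error of about √(0.95·0.05/10,000) = 0.2 points. Making cigarettes per day no stronger than the other factors changes little: 0.5/0.5/0.5 gives 94.9 vs. 95.5%, and 0.5/0.5/0.8 gives 95.1 vs. 95.4%.

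At 80 per group, power runs from 80.6 vs. 81.1% to 81.8 vs. 85.2%.

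Type I error at 250, with the null at 12% and 20%, is 3.7–5.1% unadjusted and 4.7–5.3% adjusted. A second simulation (2,000 trials) with stronger effects, log odds ratios of 1.1, 1.1 and 1.6 in size, gave 2.7% unadjusted and 4.2% adjusted.

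**3. Call-count model.** Section M says "This sample size would also offer 80% power to detect a small effect size of intervention group". Take that 80% as given and let R² be the share of outcome variance explained by the factors (assumed). Under stratified allocation the unadjusted statistic has variance 1 − R², so:

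- size, unadjusted = 2Φ(−1.96/√(1−R²))
- power, unadjusted = Φ(0.842/√(1−R²))
- power, adjusted = Φ(2.802/√(1−R²) − 1.96)

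For R² = 0.05, √0.95 = 0.975. Unadjusted power is Φ(0.864) = 80.6%, adjusted power is Φ(0.915) = 82.0%, and unadjusted size is 2Φ(−2.011) = 4.4%.

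| R² | Gain in power (points) | Unadjusted size |
|---|---|---|
| 0 | 0 | 5.0% |
| 0.02 | 0.5 | 4.8% |
| 0.05 | 1.4 | 4.4% |
| 0.10 | 2.7 | 3.9% |

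Simulation with an assumed 0–5 call distribution and a linear model at 250 gives gains of 0.1, 0.5, 1.4 and 3.0 points.

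**4. Open covariate list.** Null at 20%, 250 participants, seven covariates at an assumed 0.3 or 0.4 log-odds per SD:
- Keeping prognostic covariates (p<0.05) gives 5.0–5.2% type I error.
- Keeping imbalanced covariates (p<0.10) gives 4.2–4.7%.
- Fixing the three factors gives 4.9–5.1%.

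Inflation appears only if the model is chosen on the treatment result. Taking the smaller p of the unadjusted and all-seven models gives 6.4–6.6%, and the extreme of the smallest p over all 128 models gives about 9–11%. Nothing in the documents suggests such conduct.

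**5. Can the model be fitted?** Expected abstinent participants: 125·(0.12 + 0.30) = 52.5, or about 13 for each of four terms. The smallest of the eight cells would hold about 250·0.50·0.32·0.35 = 14 people, so main effects are preferable to cell indicators.

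**The case against.** The strongest reply is that nothing in the plan fails. Omitting the factors does not inflate type I error, and unadjusted power stays at or above the stated 80% throughout: 94.6–95.4% at 250, 80.6–81.8% at 80 per group, and 81.3% in the call model at R² = 0.10. What is lost is a possible gain, and its size rests on assumed effects whose range includes none. This is a pilot, and the list already permits adjustment for two of the factors. All of that stands, and it is why the point is rated low.

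Two qualifications also stand:
- **Conservatism depends on allocation that balances the factors.** In a simulation with unrestricted allocation, unadjusted size was 4.7–4.9%, essentially nominal, although a power gain of 0.3–2.1 points at 250 remained. Section D does state stratified randomization, so the balanced case applies, but the block size is assumed.
- **Treating all 250 as analysed relies on the Aim 1 rule** that non-verified participants count as smoking ("no need to account for loss to follow-up"). That rule is worded for biochemical verification, which has been dropped, and the text does not say how it carries over to self-report.

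Neither removes the mismatch between sections D and M.

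**Conclusion.** The concern holds, at low severity. As written, the plan allows a primary model that ignores the factors it randomizes by, and the cigarettes-per-day factor is not among the listed covariates. Adjusting is worth about 0.1 to 1 point of power for abstinence at 250, about 0.5 to 3.5 points at 80 per group, and 0 to 2.7 points for call counts. It also brings type I error back to about 5% where the unadjusted test is conservative. These sizes rest on assumed prognostic strengths, strata shares, equal allocation and blocks of 4. The direction does not depend on their exact values. The stated sample size is unaffected.

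**What to change.** Add to section M, Aim 2, before outcome data are examined:

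> The primary logistic model and the call-count model (linear, or the count model used in its place) will include treatment group and the three randomization factors as randomized (sex, White/non-White, ≤10 vs. >10 cigarettes per day) as main effects. Models adding other listed covariates are sensitivity analyses. Unadjusted abstinence rates by arm and the marginal risk difference with 95% CI will also be reported, because the adjusted odds ratio is conditional on the factors.

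If a zero-inflated model remains an option, state which part or parts of it carry the factors.

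The cost is a few sentences and no new data, since the factors must be known in order to randomize. The one side effect is on the odds ratio. The marginal value is (0.30/0.70)/(0.12/0.88) = 3.14, and it becomes 3.23–3.61 when conditional on the factors under the assumed effects. Hence the request for the marginal risk difference. Its 95% half-width at 125 per arm is about 1.96·√[(0.12·0.88 + 0.30·0.70)/125] = 9.8 points.
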